5.4 Treatment adherence

The PI will determine when lack of adherence to the study protocol should lead to removal from study. The patient removed for lack of adherence will still be included in the ITT analysis.

5.5 Discontinuation of treatment

Discontinuation of the fulvestrant plus Palbociclibor tamoxifen plus Palbociclib will occur in the case of unacceptable toxicity, disease progression, patient's own request, treating physician's discretion or if the study is closed.

5.6 Procedures for discontinuation of a subject from treatment

All patients who initiate protocol treatment will be included in the overall evaluation of response as part of the ITT analysis. All reasons for discontinuation of treatment should be documented clearly in the study record. In case of treatment discontinuation due to unacceptable toxicity as defined in section 6.4, the patients will still be included in the overall evaluation of response by ITT. If the study medication is discontinued at the patient's own request, the reason for discontinuation from the study must be documented and the patient followed for outcomes by ITT analysis.

5.7 Training of study site personnel

The participating sites will provide experienced staff, and adequate equipment and facilities to support this clinical trial. The participating sites will also be responsible for research staff training in computer applications, human subject research, and HIPAA compliance, as well as the continuing education in these areas as required by local institutional standards.

5.8 Withdrawal from study

Withdrawal from study may occur at patient's own request. The reason for discontinuation from the study must be documented. The patients will be included in the overall evaluation of response by ITT. The patient's permission for active and passive follow-up will be sought, with response censored at the time of study withdrawal only if the patient withdraws consent for any follow-up.

6. COLLECTION OF STUDY VARIABLES

6.1 Recording of data

All information will be collected on study-specific case report forms by the study staff at each institution. The necessary forms will be provided to each site by the UPMC Hillman Cancer Center CRSCC. The

Coordinating Center staff will enter the data required by the protocol within 10 days into the Electronic Case Report Forms (eCRF). The Principal Investigator is responsible for assuring

that the data entered into eCRF is complete, accurate, and that entry and updates are performed in a timely manner.

6.2 Data collection at enrollment and follow-up

The completed forms will be forwarded via email or fax to the Coordinating Center for central review and inclusion in the study dataset with relevant source documentation as outlined in the case report forms. The data submission schedule is as follows:

1. At the time of registration:
 - a. Registration Forms
 - b. Informed Consent Form (signed by the subject and approved investigator)
 - c. Eligibility Checklist
 - d. Source documents related to eligibility and randomization
 - e. Research tissue samples with documentation, if baseline tumor biopsy is collected.

2. At the start of each new cycle:
 - a. Adverse event forms
 - b. Drug diary (both arms)
 - c. Study blood along with documentation (sent on same day of draw)
 - d. Pertinent medication list

3. Final Assessment (off-treatment):
 - a. AE form
 - b. Pertinent source documents
 - c. Research tissue/blood samples with documentation

4. Follow-up (disease status, survival every 3 months)

All study data will be reviewed for completeness and accuracy by the Protocol Chair or his/her designee. The Principal Investigator (or his/her designee) at each respective institution is responsible for review, and ensuring the completeness and accuracy, of the data generated by his/her institution.

Peripheral blood collected during the study will be sent to UPMC Magee-Womens Research Institute for analysis of ESR1 mutation. Solid tumor biopsies will be sent to the Magee-Womens Hospital of UPMC Department of Pathology for analysis. When solid tumor biopsies are obtained, one core will be sent for MammoSeq testing, which will include ESR assessment as well as other genes described above. This test will be performed at the Division of Molecular Genomic Pathology of UPMC Magee-Womens Hospital. The other core will be used for the NanoString studies. A 3rd core, if obtained, will be banked as fresh frozen tissue to be used in the event that the two (2) other core biopsy samples do not contain sufficient usable tissue for either analysis of ESR1 mutation and/or MammoSeq testing .

6.3 Efficacy

Response and progression will be evaluated in this study using the international criteria proposed by the revised Response Evaluation Criteria in Solid Tumours (RECIST) Committee (version 1.1). Changes in only the largest diameter (unidimensional measurement) of the tumor lesions are used in the RECIST criteria. Patients will be evaluated for response after every 2 cycles of therapy. In the case of non-measurable disease (as defined in 6.3.2), progression of disease will be determined by the appearance of new metastatic lesions or clinical worsening secondary to the non-measurable metastatic site at the treating physician's discretion.

6.3.1 Measurable systemic disease

Tumor lesions: Must be accurately measured in at least one dimension (longest diameter in the plane of measurement is to be recorded) with a minimum size of:

- 10mm by CT scan (CT scan slice thickness no greater than 5 mm).
- 10mm calliper measurement by clinical exam (lesions which cannot be accurately measured with callipers should be recorded as non-measurable).
- 20mm by chest X-ray.

Malignant lymph nodes: To be considered pathologically enlarged and measurable, a lymph node must be ≥ 15 mm in short axis when assessed by CT scan (CT scan slice thickness recommended to be no greater than 5 mm). At baseline and in follow-up, only the short axis will be measured and followed.

6.3.2 Non-measurable disease

All other lesions, including small lesions (longest diameter < 10 mm or pathological lymph nodes with ≥ 10 to < 15 mm short axis) as well as truly non-measurable lesions. Lesions considered truly non-measurable include: leptomeningeal disease, ascites, pleural or pericardial effusion, inflammatory breast disease, lymphangitic involvement of skin or lung, abdominal masses/abdominal organomegaly identified by physical exam that is not measurable by reproducible imaging techniques.

Special considerations regarding lesion measurability

Bone lesions, cystic lesions, and lesions previously treated with local therapy require particular comment:

Bone lesions:

- Bone scan, PET scan or plain films are not considered adequate imaging techniques to measure bone lesions. However, these techniques can be used to confirm the presence or disappearance of bone lesions.
- Lytic bone lesions or mixed lytic-blastic lesions, with identifiable soft tissue components, that can be evaluated by cross-sectional imaging techniques such as CT or MRI can be considered as measurable lesions if the soft tissue component meets the definition of measurability described above.
- Blastic bone lesions are non-measurable.

Cystic lesions:

- Lesions that meet the criteria for radiographically defined simple cysts should not be considered as malignant lesions (neither measurable nor non-measurable) since they are, by definition, simple cysts.
- ‘Cystic lesions’ thought to represent cystic metastases can be considered as measurable lesions, if they meet the definition of measurability described above. However, if non-cystic lesions are present in the same patient, these are preferred for selection as target lesions.

Lesions with prior local treatment:

- Tumor lesions situated in a previously irradiated area, or in an area subjected to other loco-regional therapy, are usually not considered measurable unless there has been demonstrated progression after local treatment.

6.3.3 Specifications by methods of measurements

Measurement of lesions

All measurements should be recorded in metric notation, using callipers if clinically assessed. All baseline evaluations should be performed as close as possible to the treatment start and never more than 28 days before the beginning of the treatment.

Method of assessment

The same method of assessment and the same technique should be used to characterise each identified and reported lesion at baseline and during follow-up. Imaging based evaluation should always be done rather than clinical examination unless the lesion(s) being followed cannot be imaged but are assessable by clinical exam.

Clinical lesions: Clinical lesions will only be considered measurable when they are superficial and ≥ 10 mm diameter as assessed using callipers (e.g., skin nodules). For the case of skin lesions, documentation by color photography including a ruler to estimate the size of the lesion is suggested. When lesions can be evaluated by both clinical exam and imaging, imaging evaluation should be undertaken since it is more objective and may also be reviewed at the end of the study.

Chest X-ray: Chest CT is preferred over chest X-ray, particularly when progression is an important endpoint, since CT is more sensitive than X-ray, particularly in identifying new lesions. However, lesions on chest X-ray may be considered measurable if they are clearly defined and surrounded by aerated lung.

CT, MRI: CT is the best currently available and reproducible method to measure lesions selected for response assessment. Guidelines have defined measurability of lesions on CT scan based on the assumption that CT slice thickness is 5mm or less. When CT scans have slice thickness greater than 5 mm, the minimum size for a measurable lesion should be twice the slice thickness.

MRI is also acceptable in certain situations (e.g. for body scans).

Ultrasound: Ultrasound is not useful in assessment of lesion size and should not be used as a method of measurement. Ultrasound examinations cannot be reproduced in their entirety for

independent review at a later date and, because they are operator dependent, it cannot be guaranteed that the same technique and measurements will be taken from one assessment to the next. If new lesions are identified by ultrasound in the course of the study, confirmation by CT or MRI is advised. If there is concern about radiation exposure at CT, MRI may be used instead of CT in selected instances.

Endoscopy, laparoscopy: The utilisation of these techniques for objective tumor evaluation is not advised. However, they can be useful to confirm complete pathological response when biopsies are obtained or to determine relapse in trials where recurrence following complete response or surgical resection is an endpoint.

Tumor markers: Tumor markers alone cannot be used to assess objective tumor response. If markers are initially above the upper normal limit, however, they must normalise for a patient to be considered in complete response.

Cytology, histology: These techniques can be used to differentiate between PR and CR in rare cases if required by protocol (for example, residual lesions in tumor types such as germ cell tumors, where known residual benign tumors can remain). When effusions are known to be a potential adverse effect of treatment (e.g. with certain taxane compounds or angiogenesis inhibitors), the cytological confirmation of the neoplastic origin of any effusion that appears or worsens during treatment can be considered if the measurable tumor has met criteria for response or stable disease in order to differentiate between response (or stable disease) and progressive disease.

6.3.4 Response Assessment

Target Lesions

When more than one measurable lesion is present at baseline all lesions up to a maximum of five lesions total (and a maximum of two lesions per organ) representative of all involved organs should be identified as **target lesions** and will be recorded and measured at baseline (this means in instances where patients have only one or two organ sites involved a maximum of two and four lesions respectively will be recorded).

Evaluation of Target Lesions

- Complete Response (CR): Disappearance of all target lesions. Any pathological lymph nodes (whether target or non-target) must have reduction in short axis to <10 mm.
- Partial Response (PR): At least a 30% decrease in the sum of diameters of target lesions, taking as reference the baseline sum diameters.
- Progressive Disease (PD): At least a 20% increase in the sum of diameters of target lesions, taking as reference the smallest sum on study (this includes the baseline sum if that is the smallest on study). In addition to the relative increase of 20%, the sum must also demonstrate an absolute increase of at least 5 mm. (Note: the appearance of one or more new lesions is also considered progression).
- Stable Disease (SD): Neither sufficient shrinkage to qualify for PR nor sufficient

increase to qualify for PD, taking as reference the smallest sum of diameters while on study.

Non-target lesions

All other lesions (or sites of disease) including pathological lymph nodes should be identified as **non-target lesions** and should also be recorded at baseline. Measurements are not required and these lesions should be followed as ‘present’, ‘absent’, or in rare cases ‘unequivocal progression’. In exceptional circumstances, unequivocal progression in non-target lesions may be accepted as disease progression. In addition, it is possible to record multiple non-target lesions involving the same organ as a single item on the case record form (e.g. ‘multiple enlarged pelvic lymph nodes’ or ‘multiple liver metastases’).

When the patient only has non-measurable disease, the increase in overall disease burden should be comparable in magnitude to the increase that would be required to declare PD for measurable disease: i.e., an increase in tumor burden from “trace” to “large”, an increase in nodal disease from “localized” to “widespread”, or an increase sufficient to require a change in therapy.

Evaluation of Non-Target Lesions

- Complete Response (CR): Disappearance of all non-target lesions and normalisation of tumor marker level. All lymph nodes must be non-pathological in size (<10mm short axis).
- Non-CR/Non-PD: Persistence of one or more non-target lesion(s) and/or maintenance of tumor marker level above the normal limits.
- Progressive Disease (PD): Unequivocal progression of existing non-target lesions. (Note: the appearance of one or more new lesions is also considered progression).

Evaluation of Best Overall Response

The best overall response is the best response recorded from the start of the treatment until disease progression/recurrence (taking as reference for progressive disease the smallest measurements recorded since the treatment started). The patient’s best overall response assignment will depend on the findings of both target and non-target disease and will also take into consideration the appearance of new lesions.

TABLE 2. Time to response definition

Target Lesions	Non-Target Lesions	New Lesions	Overall Response
-----------------------	---------------------------	--------------------	-------------------------

CR	CR	No	CR
CR	Non CR/Non PD	No	PR
CR	Not evaluated	No	PR
PR	Non PD or not all evaluated	No	PR
SD	Non PD or not all evaluated	No	SD
Not all evaluated	Non PD	No	NE
PD	Any	Yes or no	PD
Any	PD	Yes or no	PD
Any	Any	Yes	PD

CR= complete response, PR= partial response, PD= progressive disease, SD= stable disease, NE= not evaluable.

Note: Patients with a global deterioration of health status requiring discontinuation of treatment without objective evidence of disease progression at that time should be reported as “*symptomatic deterioration*”. Every effort should be made to document the objective progression even after discontinuation of treatment.

Progression Free Survival

PFS is defined as the duration of time from time of randomization to time of progression or death, whichever occurs first. PFS for a subject without an event will be censored on the date of last tumor assessment. If an interval of 6 months passes without a tumor assessment, PFS will be censored at the time of the earlier tumor assessment, even if an event (progressive disease or death) is later observed.

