2.2 Secondary objectives

1. Collection of clinical outcome data in this limited patient population
 - a. Progression free survival (PFS), Objective response rate (ORR) and Clinical benefit rate (defined as CR+PR+ stable disease at any tumor assessment) and clinical benefit rate at 6 months (CBR6) (defined as CR+PR+ stable disease for at least 6 months) in the entire cohort, and the ESR1-mt cohorts
2. Correlation between longitudinal changes in circulating levels of ESR1 mutations and clinical outcome
3. Assessment of concordance of ESR1 status in plasma and biopsy samples
4. Use of cfRNA to determine gene expression in AI resistant mutant ESR1 MBC

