5.3 Restrictions and concomitant therapies during the study

The following restrictions apply during the entire duration of the study:

1. No other investigational therapy is allowed during the study period. If an investigational therapy was used prior to study enrollment, a washout period of 28 days is required before enrollment.
2. No anticancer agents other than the study medications may be given to patients during the study period, with the following exceptions:
 1. Bisphosphonates, Zometa (zoledronic acid), or Xgeva (Denosumab)
 2. GnRH analog agents.
3. If any other anticancer agents are required for a patient then the patient must first be withdrawn from the study.
4. Concurrent radiation therapy is prohibited, however palliative radiotherapy may be considered on a case by case basis after discussion with the Study Chair.
5. Grapefruit and other citrus juices affect P450 and PgP activity. Concomitant use will be avoided. All CYP3A4 inducers and inhibitors should be avoided.
6. Medications that inhibit or induce CYP2D6, CYP2C8/9 and CYP2D6 will be avoided and used at the discretion of the principal investigator or treating physician on a case by case basis. Please see appendix A for a list of these medications.
7. Anticoagulant medications can be used during the study period. The appropriate PT, INR and PTT levels will be determined at the discretion of the treating physician.

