11. EVALUATION AND CALCULATION OF VARIABLES

11.1 Calculation or derivation of efficacy variable(s)

The primary objectives of the study are descriptive assessments of ESR1 mutation detection in plasma. One of the secondary endpoints of the study is PFS. PFS is defined as the duration of time from time of randomization to time of progression or death, whichever occurs first. PFS for a subject without an event will be censored on the date of last tumor assessment. If an interval of 6 months passes without a tumor assessment, PFS will be censored at the time of the earlier tumor assessment, even if an event (progressive disease or death) is later observed. If a patient has not had an event, PFS will be censored at the date of the last adequate tumor evaluation. PFS will also be censored at the date of tumor evaluation when the next tumor evaluation (or death) is >6 months after the previous evaluation without an event. PFS will be assessed via local radiology assessment according to RECIST 1.1.

Although central review may occur as part of site calibration or an audit, the local assessment will be considered as the basis for the primary efficacy analysis. In the absence of measurable disease at baseline, the following criteria (per RECIST 1.1) will be used to assess disease progression among the patients with nonmeasurable lytic or mixed (lytic + blastic) bone lesions: 1) The appearance of one or more new lesions or 2) Unequivocal progression of existing non-measurable lesions.

Additional secondary endpoints include response rate, clinical benefit rate, (defined as CR+PR+ SD at any tumor assessment), clinical benefit rate at 6 months (CBR6), in the entire cohort, and the ESR1-mut cohorts. Response rate will be reported from best overall response according to RECIST 1.1 and as described in section 6.3. The response rate will then be compared amongst the tamoxifen plus palbociclib and fulvestrant plus palbociclib arms in the entire cohort and in the subgroup of ESR1-mt patients.

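### Best overall response is not cut off when another anticancer therapy starts, so a response or six-month stability on that therapy can count for the randomised arm in ORR and CBR6

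*Combined protocol and SAP*

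**What the plan says.** All references are to the combined protocol and SAP.

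- **Response window (6.3.4):** "The best overall response is the best response recorded from the start of the treatment until disease progression/recurrence". No other end point is given.
- **Response rate (11.1):** "Response rate will be reported from best overall response according to RECIST 1.1 and as described in section 6.3".
- **Clinical benefit (2.2):** "Clinical benefit rate (defined as CR+PR+ stable disease at any tumor assessment"; CBR6 requires stable disease lasting at least 6 months. Neither definition mentions later therapy.
- **Other anticancer agents (5.3, item 3):** "If any other anticancer agents are required for a patient then the patient must first be withdrawn from the study".
- **Response at study withdrawal (5.8):** patients stay in the response evaluation, "with response censored at the time of study withdrawal only if the patient withdraws consent for any follow-up".
- **Who is analysed (5.6):** "All patients who initiate protocol treatment will be included in the overall evaluation of response as part of the ITT analysis".
- **Stopping without progression (5.5):** toxicity, patient request and physician discretion are all listed reasons.
- **After treatment (9.1, Table 4 and its notes):** disease status and survival are followed about every 3 months until death, by visit, telephone or chart review. CT is optional at the off-treatment and follow-up visits.
- **Radiotherapy (5.3, item 4):** it is prohibited while on study, except that "palliative radiotherapy may be considered on a case by case basis after discussion with the Study Chair". Section 6.3.2 covers irradiated lesions only under the heading of prior local treatment, as a question of measurability.

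**The concern.** ORR and CBR6 are meant to describe what fulvestrant plus palbociclib and tamoxifen plus palbociclib achieve. If the window stays open after a patient moves to another anticancer agent, tumour shrinkage or stability produced by that agent is counted for the randomised arm.

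Section 11.1 compares response between arms, overall and in ESR1-mt patients. Section 12.2 looks for a signal of clinical benefit confined to ESR1-mt patients on fulvestrant. With groups this small, a single misattributed patient visibly changes the reported rate. The trial is open label (3.2) and assessment is local (11.1). If the rule is not fixed beforehand, such patients would have to be settled case by case with the arm known.

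**Working it through.** The plan gives no assumed response rate, power or alpha for response, so there is no design figure to reproduce. The check is a reading of the rules together, followed by scale.

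**1. Is there a cut at new therapy anywhere?**

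- 6.3.4 ends the window at progression only, and 11.1 takes the response rate from that definition.
- 5.3 item 3 requires withdrawal before another agent. This governs conduct and does not say that later data are excluded.
- 5.8, the only text on response after withdrawal, cuts it only when all follow-up is refused.
- 5.6 settles the denominator. It does not say which scans count.

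The window therefore stays open for a patient who changes therapy without progression and accepts follow-up.

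**2. Two constructed records**

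| Record | As written | Cut at new therapy |
|---|---|---|
| A: SD at week 8, stops for toxicity at week 12, starts another agent, first PR at week 24 | Best response PR | Best response SD |
| B: SD at week 8, stops at week 12, starts another agent, still SD at a scan beyond 6 months | CBR6 met | CBR6 not met |

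Both records already have SD on study treatment at week 8, so both count towards CBR at any assessment under either rule. Only a patient with no qualifying on-study assessment could gain that endpoint from the next therapy. Record B needs no response to the new agent, only absence of progression, so CBR6 is the more exposed endpoint.

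**3. Weight of one patient**

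- Arm size is 20 (12.2): 1/20 = 5 percentage points.
- ESR1-mt prevalence is hypothesised at 25% (6.3.5): 20 × 0.25 = 5 per arm, and 1/5 = 20 points.

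**4. How many patients? (assumptions; the documents give none of these rates)**

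- Suppose 10–20% stop without progression and 20–30% of them respond to the next therapy: 20 × 0.10 × 0.20 = 0.4, and 20 × 0.20 × 0.30 = 1.2 per arm.
- That calculation takes everyone who stops to start new therapy before progression, have measurable disease, be scanned, and have no earlier response on study. It is closer to an upper bound than an expectation.
- Allow 65% with measurable disease (4.1 admits non-measurable disease) and 50% scanned after stopping: 0.4 × 0.65 × 0.50 = 0.13, and 1.2 × 0.65 × 0.50 = 0.39 per arm. Divided by 20, this is 0.65 to 1.95 points of ORR.
- For CBR6, the same stopping and scanning assumptions give 20 × 0.10 × 0.50 = 1 to 20 × 0.20 × 0.50 = 2 per arm who stop and are scanned. That is before requiring that they stopped before 6 months, began another agent without progression, and were still stable at 6 months. These last fractions cannot be estimated from the documents.

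**The case against.** The best counter-argument is that response assessment is tied to study therapy. Section 6.3 evaluates response after every 2 cycles, treatment normally runs to progression (3.1), and by then the window has closed. After treatment, CT is optional and disease status may come from a telephone call or chart review, so no formal response assessment is required. This stands, and it limits the number of patients affected. It does not close the window for those who are scanned.

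A second argument is that 5.8 is worded around withdrawal at the patient's own request, so it may not govern withdrawal under 5.3. Even then, nothing else supplies a cut, and 6.3.4 still runs to progression.

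A reader might infer more than the documents support:

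- **That ORR is inflated by 2 to 6 points.** This is 0.4 to 1.2 patients out of 20. It rests on assumed rates and omits optional imaging and non-measurable disease. It is also an inflation within an arm. Similar inflation in both arms would largely cancel in the difference, and no differential can be estimated.
- **That clinical benefit in general is distorted.** CBR at any assessment is barely touched, as both records show.
- **That 5.6 makes later scans count.** It only keeps patients in the analysis.
- **That one patient could turn a non-significant comparison significant.** With assumed counts, 10/20 vs 4/20 gives a mid-P of 0.057 and 11/20 vs 4/20 gives 0.028. The plan sets no alpha for response, and its only threshold for calling fulvestrant promising uses the PFS hazard ratio (12.1).
- **That shrinkage of a lesion irradiated on study is scored wrongly.** The documents do not say what the right score is. They only lack a rule, for what is an exception to a prohibition.

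**Conclusion.** The point holds, and it is minor. As written, a first PR or CR, or stable disease carried to 6 months, on a subsequent anticancer therapy can count in ORR or CBR6 for the randomised arm. The withdrawal rule in 5.3 does not prevent this, because 5.8 keeps response open unless all follow-up is refused.

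Each such patient is worth 5 points in an arm of 20, or about 20 points among about 5 ESR1-mt patients per arm if prevalence is 25%. The expected number is probably below one per arm. For responses this follows from the assumed rates once measurability and scanning are allowed for (0.13 to 0.39). For CBR6 it is a judgement. ORR and CBR6 are secondary, 11.1 calls the primary objectives descriptive, and external constraints set the sample size, so no design figure changes.

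**What to change.** - **6.3.4 and 11.1:** derive best overall response, ORR, CBR and CBR6 only from assessments up to the earlier of progression or the start of any subsequent anticancer therapy. Keep every patient in the denominator. Leave the PFS rule unchanged.
- **5.8:** amend the sentence on censoring of response to agree. Otherwise the two sections would contradict each other.
- **CRF:** record the start date of subsequent anticancer therapy. The follow-up item in 6.2 lists only disease status and survival.
- **SAP:** state how a target lesion given palliative radiotherapy on study is scored for CR and PR, for example by not crediting its shrinkage after that date, and record the radiotherapy date. This is a scoring rule and leaves open whether such treatment is given.

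The cost is a few sentences and two date fields. The downside is that a few late responses no longer count, including any that were in truth a delayed effect of study treatment.
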